## 1.0 TRIAL SUMMARY

Abbreviated Title	SRS and Pembrolizumab for Melanoma and Non-Small Cell Lung Cancer (NSCLC) brain metastases (BM).
Trial Phase	Pilot Study
Clinical Indication	Melanoma and NSCLC Brain Metastases
Trial Type	Pilot study with three different radiation dose cohorts.
Type of control	None
Route of administration	Pembrolizumab delivered 200 mg IV every 3 weeks +/- 7 days for at least 2 years, or until progression.
Trial Blinding	N/A
Treatment Groups	All receive pembrolizumab 200 mg IV every 3 weeks +/- 7 days until progression or at least 2 years, with 3 altered radiation dose fractionation groups delivered during first cycle of pembrolizumab.
Number of trial subjects	30 patients.
Estimated enrollment period	2 years
Description of enrollment	
In 2013, we delivered SRS to 20 metastatic melanoma brain metastases patients and 27 NSCLC BM patients. In 2014, we delivered SRS to 14 and 26 patients, respectively. Assuming similar numbers over the next two years, and accruing 45% of patients, we anticipate around 30 patients to enroll.
 
These projected accrual numbers do not reflect the possibility of increased patient referrals from our satellite facilities, and/or increased regional/national referrals, once the trial is opened. We are also not aware of other potentially competing radiation SRS for melanoma and NSCLC brain metastases trials at our institution at this time.

Duration of Intervention	At least 12 months of Pembrolizumab, or until progression.
Duration of Evaluation	3 year ( 2 yrs during accrual, and at least 1 year follow-up for last patient accrued on the study)
Estimated duration of trial	3 years (2 years to accrue + 1 years to follow all patients)
Duration of Participation	3 years
Study Center	Emory University. Atlanta, Georgia.

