### **3.2 Secondary Objective(s), Endpoint(s) & Hypothesis(es)**

#### **3.2.1 Secondary Objectives**

- b. To evaluate intracranial outcomes – control of the treated lesion in the brain with SRS+ pembrolizumab (i.e. local control), development of additional sites of disease in the brain that were not initially treated with SRS (i.e. anywhere intra-cranial failure), intra-cranial progression free survival (local control of the area that received SRS and anywhere intra-cranial failure), extra-cranial disease response (overall progression free survival), rate of leptomeningeal dissemination, and overall survival.
- c. To determine the overall response rate and overall survival of combination SRS and pembrolizumab compared to:
  - i. SRS alone (historical control)
  - ii. Pembrolizumab alone (historical control)
- d. To evaluate treatment response at un-irradiated and extra-cranial sites (i.e. the abscopal effect) with all three arms;
- e. To compare differences in potential immune biomarkers, pretreatment, during treatment, and post treatment;

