### **3.2.4 Secondary Hypotheses**

- a. Using descriptive analyses, combination therapy will result in a higher median survival relative to a historical cohort treated with pembrolizumab alone or SRS alone.
- b. Using descriptive analyses, combination therapy, relative to pembrolizumab alone cohort, will result in higher local control and intracranial control.
- c. Using descriptive analyses, combination therapy, relative to the cohort treated with pembrolizumab alone, will result in a higher improved RECIST and immune RECSIT response rate.
- d. We may see early difference in patients that develop enhanced abscopal response from those that do not, based on early biomarker analysis, and that this could potentially guide future therapy selection.
- e. Radiation necrosis rates may be same, or better with altered dose fractionation compared with single fraction, especially when combined with concurrent PD1;

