The radiation dose arm which meets the lowest acute and late toxicity endpoints, but also potentially provided a higher overall systemic response rate, will be considered the best radiation dose level that can be combined with pembrolizumab. Our published series of melanoma patients undergoing SRS alone had an average survival of 38.5% at 1 yr (Patel KR et al, American J. Clinic. Oncology. 2015, May 16. Epub); Our recent multi-institutional review in collaboration with Duke University suggested 1 yr overall survival of 78% for patients undergoing SRS and PD1 in combination (not published, accepted for annual presentation at American Society of Radiation Oncology Meeting, 2016). Thus, we suspect an improvement of 40% in OS compared with SRS alone. With 12 patients on the most immunogenic arm (9Gy x 3), we would be expected to have lowest acute and late toxicity as well as potentially the highest OS benefit and would likely be the arm for a future trial.

With 12 patients per group, a 2-year accrual time with an additional 1 year of follow-up (3 total years), we have 72% power to detect a difference in survival of 40% (78% vs. 38%) at 1 year.

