#### **14.2 Study Design for Expansion Cohort Phase**

After the initial pilot phase with 6 patients per radiation dose arm, patients will then be enrolled into the expansion cohort (6 more patients) and treated assuming toxicity is acceptable during the initial enrollment period of the first 6 patients on each arm. This would bring the total

**Product:** Pembrolizumab (MK-3475)

64

**Protocol/Amendment No.:** Rad3179-16 (MK-3475-423), v.6/23/17

patients up to 12 per radiation dose arm: (Arm A: 6 patients total, Arm B: 12 patients, Arm C: 12 patients), for a total of 30 patients for all 3 different radiation dose arms.

The total number of patients enrolled in the entire trial will thus depend on the RTOG grade 3 CNS acute toxicity seen on each of the dose arms. If no DLT are identified, then the minimum number of patients in the expansion cohort will be 30; if each cohort has a DLT, then the maximum number of patients enrolled in the dose escalation phase is 12 (6 patients X 2 different radiation dose arms). Therefore, the range of patients to be enrolled in this study is expected to be 18-30. The expansion of arm A is stopped. Arm B and C will continue to enroll, as is currently designed.

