#### **14.3.3 Overall Survival**

For overall survival, death from any cause will be defined as the event. Patients will be censored at time of last follow-up. OS will be estimated using the Kaplan-Meier product-limit method.

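### The 72% survival power in Section 14.1.2 belongs to no test or contrast in this trial: there is no SRS-alone group, and survival is only estimated

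*Combined protocol and SAP*

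**What the plan says.** The last paragraph of Section 14.1.2 assumes 12 patients per group, 2 years of accrual and 1 further year of follow-up, and concludes that "we have 72% power to detect a difference in survival of 40% (78% vs. 38%) at 1 year". The paragraph before it gives the source of the two rates. The lower is from the institution's own melanoma series treated with SRS alone, the higher from an unpublished multi-institutional review of SRS with PD-1 inhibition. The expected gain is described as relative to SRS alone.

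Other sections describe the design and the survival analysis:

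- **Section 1.0** gives the type of control as none. All patients receive pembrolizumab, "with 3 altered radiation dose fractionation groups delivered during first cycle of pembrolizumab". Section 6.2 says randomization does not apply.
- **Section 14.2** gives the arm sizes: "Arm A: 6 patients total, Arm B: 12 patients, Arm C: 12 patients".
- **Section 3.2.1** lists SRS alone as a historical control for response and survival.
- **Section 3.2.4** frames the hypothesis as "Using descriptive analyses, combination therapy will result in a higher median survival relative to a historical cohort treated with pembrolizumab alone or SRS alone".
- **Section 14.3.3** says "OS will be estimated using the Kaplan-Meier product-limit method". It names no test and no confidence interval.

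**The concern.** Power is a property of a specified test of a specified contrast. Here the contrast is combination against SRS alone, and no enrolled group receives SRS alone. Arms B and C are the only 12 versus 12 pair, but both receive the combination, so 78% versus 38% does not describe the difference between them. Alpha, sidedness and the test are not given for survival anywhere in the plan.

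A reader could take 72% as the trial's chance of showing a survival gain over SRS alone. That matters because survival is not incidental here. Section 2.3 uses overall survival in naming the best radiation dose level, and Sections 2.3 and 14.1.2 point to the 9 Gy x 3 arm for a future trial, partly on an expected survival benefit. A stated power makes that choice look as if it rests on a formal, reasonably powered comparison.

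**Working it through.** **Inputs.** From Section 14.1.2: 1-year survival 78% and 38%, 12 per group, accrual A = 2 years, further follow-up F = 1 year. The same section gives the series result as 38.5%, so both values are used. Assumed because not stated: exponential survival, uniform accrual, no dropout, 5% alpha.

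**Reproducing the 72%.**

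- Hazards: λ1 = −ln 0.78 = 0.248; λ0 = −ln 0.38 = 0.968. Hazard ratio = 0.248/0.968 = 0.257 (unrounded hazards).
- Probability of an observed death: 1 − [exp(−λF) − exp(−λ(A+F))]/(λA), which gives 0.385 and 0.832.
- Expected deaths: 12 × (0.385 + 0.832) = 14.6.
- Schoenfeld, two-sided 5%: Φ(√14.61/2 × |ln 0.257| − 1.96) = Φ(0.64) = 73.8%. With 38.5% the hazard ratio is 0.260 and power is 72.8%.
- Simulated log-rank test (20,000 runs): about 71% at 38% and about 70% at 38.5%.

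The stated figure is therefore consistent with a concurrent two-group log-rank test.

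**Whether the text identifies the calculation.** The same inputs (12 versus 12, 78% versus 38%, 5% alpha) give:

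| Method | Two-sided | One-sided |
|---|---|---|
| Schoenfeld | 73.8% | 83.0% |
| Freedman | 61.8% | 73.1% |
| Two proportions at 1 year, pooled | 51.1% | 64.5% |
| Fisher exact at 1 year | 39.0% | 56.7% |

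Power runs from 39% to 83% depending on choices the plan does not state. Two entries fall within 2 points of 72%.

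**What the design can deliver.** Take 12 patients with 9 alive at 1 year and no earlier censoring. The Kaplan-Meier estimate is 0.75. On the log-log scale the standard error is √(0.25/9)/0.2877 = 0.579, and exp(1.96 × 0.579) = 3.11. The limits are 0.75^3.11 = 0.41 and 0.75^(1/3.11) = 0.91, an interval about 50 points wide.

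**Who matches the benchmark.** The 38% is a melanoma rate, and NSCLC is also eligible. As an assumption, let enrolment follow the SRS caseload in Section 1.0: "In 2013, we delivered SRS to 20 metastatic melanoma brain metastases patients and 27 NSCLC BM patients" and "In 2014, we delivered SRS to 14 and 26 patients, respectively". The melanoma share is (20 + 14)/(47 + 40) = 34/87 = 39%, or 4.7 of 12. The single years give 20/47 × 12 = 5.1 and 14/40 × 12 = 4.2. Chance variation at 39% spans roughly 2 to 8 of 12.

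**A one-sample comparison, for illustration.** With 12 patients all followed to 1 year against a fixed 38%, exact binomial:

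- Success at 8 or more alive: one-sided alpha 0.042, power at 78% 89.8%.
- Success at 9 or more alive: one-sided alpha 0.010, power at 78% 73.9%.

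Neither rule is in the plan.

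**The case against.** The strongest reply is that the arithmetic is sound and the sentence does little harm. About 72% does reproduce. The trial is labelled a pilot with no control, its primary hypothesis concerns safety alone, and Section 3.2.4 calls the historical comparisons descriptive. All of this is correct, and it limits the weight of the point. It does not rescue the sentence, which sits in the analysis plan and reads as a formal claim.

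Second, Section 3.2.1 does plan a survival comparison with SRS alone. That is so, but it is a descriptive one. What is missing is a test, and without a test there is no power.

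Third, Arm A's 6 patients matter little, since the surrounding text is about the 9 Gy x 3 arm and Arms B and C do have 12 each. This stands. The defect would remain if all three arms had 12.

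Fourth, the origin of the figure may be less obscure than it looks. The sentence speaks of groups, accrual and follow-up, which points to a log-rank calculation. The one-arm rule at 9 or more of 12 comes close numerically, but it uses none of those inputs and is not a natural reading. One-sided Freedman remains a real rival.

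Fifth, the melanoma count rests on past caseload and is soft. The mismatch itself does not depend on it, because NSCLC patients are eligible.

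**Conclusion.** The concern holds. The 72% describes a concurrent 12 versus 12 comparison with an SRS-alone group that does not exist, and no survival test is planned that could carry it. The figure is not an arithmetic error: under exponential survival, uniform accrual and two-sided 5% alpha it reproduces to within about 2 points. It simply does not apply to this design.

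The trial supports a descriptive comparison with a historical series, with a per-arm interval of about 41% to 91% if 9 of 12 are alive at 1 year. That series matches only the melanoma patients, perhaps 5 of 12 if past caseload is a guide. The consequence is limited to the survival claim and to any use of it in choosing an arm for a later trial. This should be corrected, but it does not threaten the primary toxicity analysis.

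**What to change.** Delete the power sentence and put in its place in Section 14.1.2:

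> Survival comparisons with the historical SRS-alone series are descriptive. No power is claimed against that series or between arms.

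Add to Section 14.3.3:

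> 1-year Kaplan-Meier survival will be reported per arm with a 95% confidence interval (log-log). The historical benchmark will be shown beside melanoma patients only, because it comes from a melanoma series.

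Two details go with this. The benchmark appears as 38% in Section 2.3 and as both 38.5% and 38% in Section 14.1.2; one value should be used throughout. The SRS-alone objective in Section 3.2.1 is not restricted by histology, so it needs a matching note. Because a per-arm melanoma subset may be very small (4 of 5 alive gives a log-log interval of about 20% to 97%), a display pooled over arms could be added.

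If the sponsor wants to keep a power figure, it should be restated for a one-sample comparison of a named arm, with test, alpha, sidedness and benchmark, and Sections 3.2.4 and 14.3.3 amended to match. The one-sample figures above assume 12 evaluable patients and do not carry over to a smaller melanoma subset.

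The cost is one sentence removed and a few lines added, with a more modest survival claim. Sample size and the primary toxicity analysis are unaffected.

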#### **14.2 Study Design for Expansion Cohort Phase**

After the initial pilot phase with 6 patients per radiation dose arm, patients will then be enrolled into the expansion cohort (6 more patients) and treated assuming toxicity is acceptable during the initial enrollment period of the first 6 patients on each arm. This would bring the total

**Product:** Pembrolizumab (MK-3475)

64

**Protocol/Amendment No.:** Rad3179-16 (MK-3475-423), v.6/23/17

patients up to 12 per radiation dose arm: (Arm A: 6 patients total, Arm B: 12 patients, Arm C: 12 patients), for a total of 30 patients for all 3 different radiation dose arms.

The total number of patients enrolled in the entire trial will thus depend on the RTOG grade 3 CNS acute toxicity seen on each of the dose arms. If no DLT are identified, then the minimum number of patients in the expansion cohort will be 30; if each cohort has a DLT, then the maximum number of patients enrolled in the dose escalation phase is 12 (6 patients X 2 different radiation dose arms). Therefore, the range of patients to be enrolled in this study is expected to be 18-30. The expansion of arm A is stopped. Arm B and C will continue to enroll, as is currently designed.

### **14.3 Statistical Analyses**

#### **14.3.1 Safety**

Proportion of acute and late toxicity for each arm out of 12 (or 6 if no expansion) will be reported, and 95% confidence intervals will be estimated using the Clopper-Pearson method.

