**2.3 Acute Toxicity, Expansion Cohorts, and Late Toxicity Assessment:**

Once 6 patients are enrolled on any given dose level, there will be a waiting period of 3 months (i.e, at time of second post SRS MRI assessment after pembrolizumab dose (i.e, 3 months after Day 1, cycle 1); This time point of 3 months and the dose limiting toxicity (i.e. grade 3 RTOG CNS toxicity) is based on similar timeline used on earlier trial to determine the safest radiation dose. Late toxicity (radionecrosis noted on MRI images will also be analyzed at 6 months and at 1 year, but will not be used to stop enrollment on any given dose arm.);

During this 3 month waiting period, the MRI images and the patients will be assessed for any

signs or symptoms of RTOG CNS toxicity as well as early manifestations of radionecrosis.  $\geq$  Grade 3 CNS toxicity is the only DLT toxicity of principal concern. Patient can still be accrued on other dose arms during this waiting period, while data is being analyzed for safety concerns on a given radiation arm.

- If  $\leq 2/6$  patients develop a DLT on a given radiation arm, accrual on the particular dose arm will continue for another 6 patients for a total of 12 patients per dose arm. RTOG 90-05 used a 20% cutoff at 3 months as the DLT endpoint. We accept 2/6 (33%) based on a biological rationale that if there is slight increase in radiation toxicity, this may be offset by increased systemic responses through immune modulation of radiation when radiation is combined with anti PD-1 (see section 4.0 for biological rationale);
- If  $\geq 3/6$  patients develop a DLT on a given radiation dose arm, this arm will stop accrual and considered unsafe;

[figure not shown]
Late toxicity (i.e, toxicity starting after 3 months) will also be analyzed (a **secondary endpoint of trial**). The principal late toxicity of interest is symptomatic radiation necrosis. This is defined as radiographic (typically on MRI) changes consistent with radiation induced necrosis, and the patient also presenting with increased neurological symptoms. Symptomatic radiation necrosis will be recorded at 6 months and at 12 months;

- The radiation dose arm which meets the lowest DLT (i.e.  $\geq$  Grade 3 CNS Toxicity at 3 months) and late toxicity (any radiation necrosis) endpoints, but also potentially provides higher overall systemic response rate and OS, will be considered the best radiation dose level that can be combined with pembrolizumab.

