- Our published series of melanoma patients undergoing SRS alone had an average survival of 38% at 1 yr (Patel KR et al, American J. Clinic. Oncology. 2015, May 16. Epub); Our recent multi-institutional review in collaboration with Duke University suggested 1 yr overall survival of 78% for patients undergoing SRS and PD1 in combination (not published, accepted for annual presentation at American Society of Radiation Oncology Meeting, 2016). Thus, we suspect an improvement of 40% in OS compared with SRS alone. 12 patients on the most immunogenic arm (9Gy x 3), would be expected to have lowest acute and late toxicity, as well as potentially the highest OS benefit. We suspect that this may be the arm for a future trial. However, this has not been tested in any currently prospective manner.

Thus, the total enrollment will be 30 patients, and not less than 18.

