#### 3.1.3 Primary Endpoint Definitions

- RTOG grade 3 CNS toxicity is defined as irreversible severe neurological symptoms requiring medications at 3 months;

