### 7.0.2 Dose Modification, CNS toxicities

Toxicity	Hold Treatment For Grade	Timing for Restarting Treatment	Discontinue Subject
Central Nervous	2-3	Toxicity resolves to Grade 0-1.	Toxicity does not resolve within 12 weeks of last dose or inability to reduce corticosteroid to

Toxicity	Hold Treatment For Grade	Timing for Restarting Treatment	Discontinue Subject
System Necrosis		(see exception below) 	1 mg or less of dexamethasone or equivalent per day within 12 weeks.
	4	Permanently discontinue	Permanently discontinue
Seizure	2-3	Toxicity resolves to Grade 0-1	Toxicity does not resolve within 12 weeks of last dose.
	4	Permanently discontinue	Permanently discontinue
Cognitive Impairment or Cognitive Disturbance	2-3	Toxicity resolves to Grade 0-1	Toxicity does not resolve within 12 weeks of last dose or inability to reduce corticosteroid to 1 mg or less of dexamethasone or equivalent per day within 12 weeks.
	4	Permanently discontinue	Permanently discontinue
Stroke	2	Toxicity resolves to Grade 0-1	Toxicity does not resolve within 12 weeks of last dose
	3-4	Permanently discontinue	Permanently discontinue

 Patients with intolerable or persistent Grade 2 drug-related AE may hold study medication at physician discretion. Permanently discontinue study drug for persistent Grade 2 adverse reactions for which treatment with study drug has been held, that do not recover to Grade 0-1 within 12 weeks of the last dose.

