## 10.2 Subject Withdrawal/Discontinuation Criteria

Subjects may withdraw consent at any time for any reason or be dropped from the trial at the discretion of the investigator should any untoward effect occur. In addition, a subject may be withdrawn by the sponsor-investigator if enrollment into the trial is inappropriate, the trial plan is violated, or for administrative and/or other safety reasons

A subject must be discontinued from the trial for any of the following reasons:

- The subject or legal representative (such as a parent or legal guardian) withdraws consent.
- Confirmed extra-cranial radiographic disease progression
- Unacceptable adverse experiences as described in section 7, 8, and 9.
- Intercurrent illness that prevents further administration of treatment
- Investigator's decision to withdraw the subject
- The subject has a confirmed positive serum pregnancy test
- Noncompliance with trial treatment or procedure requirements
- The subject is lost to follow-up
- Completed at least 24 months of uninterrupted treatment with pembrolizumab or 35 administrations of study medication, or whichever occurs last;  
*Note: 24 months of study medication is calculated from the date of first dose. Subjects who stop pembrolizumab after 24 months may be eligible for up to one year of additional study treatment at the discretion of their treating physician, especially if their disease is clinically stable;*
- Administrative reasons
- Confirmed radiographic disease progression per RECIST criteria.
  - a. *Note: A subject may be granted an exception to continue on treatment with confirmed radiographic progression if clinically stable or clinically improved, please see Section 6.5*

The End of Treatment and Follow-up visit procedures are listed in Section 12 (Protocol Flow Chart) and Section 13. After the end of treatment, each subject will be followed for 30 days for adverse event monitoring (serious adverse events will be collected for 90 days after the end of treatment as described in Section 13.2.3.1). Subjects who discontinue for reasons other than progressive disease will have post-treatment follow-up for disease status until disease progression, initiating a non-study cancer treatment, withdrawing consent or becoming lost to follow-up. After documented disease progression each subject will be followed by telephone for overall survival until death, withdrawal of consent, or the end of the study, whichever occurs first.

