#### **13.1.1.6.3 Subsequent Anti-Cancer Therapy Status**

The investigator or qualified designee will review all new anti-neoplastic therapy initiated after the last dose of trial treatment. If a subject initiates a new anti-cancer therapy within 30 days after the last dose of trial treatment, the 30-day Safety Follow-up visit must occur before the first dose of the new therapy. Once new anti-cancer therapy has been initiated the subject will move into survival follow-up.

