#### **13.1.1.13 Withdrawal/Discontinuation**

When a subject discontinues/withdraws prior to trial completion, all applicable activities scheduled for the final trial visit should be performed at the time of discontinuation. Any adverse events which are present at the time of discontinuation/withdrawal should be followed in accordance with the safety requirements outlined in Section 8.0 - Assessing and Recording Adverse Events. Subjects who a) attain a CR or b) complete at least 24 months of treatment with pembrolizumab may stop taking the drug and discontinue the trial, at the discretion of the treating physician. After discontinuing treatment following assessment of CR, these subjects should return to the site for a Safety Follow-up Visit and then proceed to the Follow-Up Period of the study.

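### The acute DLT gate and rate count enrolled patients, with no evaluability or replacement rule, so a patient lost before 3 months lowers the observed toxicity rate; the expected effect is modest

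*Combined protocol and SAP*

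**What the plan says.** Sections 2.3, 14.1.1 and 14.1.2 start a 3-month wait once six patients are enrolled on an arm. With at most 2 of 6, the rule in 2.3 is that if "patients develop a DLT on a given radiation arm, accrual on the particular dose arm will continue for another 6 patients"; with 3 or more of 6 the arm stops and is considered unsafe. Section 14.2 has already closed the expansion of Arm A, so the gate now matters for Arms B and C. Total size is given in 2.3: "Thus, the total enrollment will be 30 patients, and not less than 18".

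Section 3.1.3 defines the DLT as a status at a fixed time: "irreversible severe neurological symptoms requiring medications at 3 months".

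Section 14.3.1 then says: "Proportion of acute and late toxicity for each arm out of 12 (or 6 if no expansion) will be reported", with Clopper-Pearson intervals. Section 14.3.4 estimates radionecrosis and symptomatic radionecrosis by cumulative incidence with death as a competing risk. It does not cover the acute DLT.

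Section 10.2 allows withdrawal of consent, removal and loss to follow-up. Under 13.1.1.6.3, "Once new anti-cancer therapy has been initiated the subject will move into survival follow-up". No section defines a DLT-evaluable patient or a safety analysis set, says whether an unassessed patient is replaced, or says how such a patient is scored.

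**The concern.** The event can be fully judged only in a patient who is assessed at 3 months, but both the gate and the reported rate divide by everyone enrolled. A patient who leaves earlier without a recorded DLT adds one to the denominator and nothing to the numerator. The error has one direction: it makes an arm look safer.

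Safety is the primary objective, and the gate turns on one patient (2 versus 3 of 6). The result decides whether six more patients are treated on Arm B or C. Acute toxicity also feeds the choice of the best arm in 2.3 and 14.1.2. With no rule written down, the scoring of an unassessed patient would be settled after the data are seen.

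**Working it through.** **The plan's own figure.** The accepted proportion is 2/6 = 33%, as stated. With six fully assessed patients and a true DLT rate p, P(arm stops) = P(X ≥ 3), X ~ Bin(6, p). This gives 17% at p = 25% (the planning rate in 4.6.3), 32% at 33% (the rate accepted there), and 66% at 50%.

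**Loss by 3 months.** The plan gives no dropout rate, so I use death alone as a gauge, with constant hazard, and treat all early deaths as due to other causes.
- 78% one-year survival (2.3, 14.1.2, combined treatment): d = 1 − 0.78^0.25 = 6.0%, or 0.36 of six patients.
- 38% one-year survival (2.3, SRS alone): d = 1 − 0.38^0.25 = 21.5%, or 1.29 of six.
- 6.7-month median (4.0.1 and Table 2, melanoma): d = 1 − 0.5^(3/6.7) = 26.7%, or 1.60 of six.

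**Gate as written.** If loss is independent of toxicity and no DLT is seen before loss, each enrolled patient contributes a DLT with probability p(1 − d):

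| True DLT rate | No loss | 78% survival |
|---|---|---|
| 25% | 17% | 15% |
| 33% | 32% | 28% |
| 50% | 66% | 60% |

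**Heavier loss, and some DLTs seen first.** At a true 50%, with half of the lost DLT patients recorded before they leave, the probability becomes p(1 − d/2):

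| Scenario (true 50%) | None seen first | Half seen first |
|---|---|---|
| 78% survival (6% lost) | 60% | 63% |
| 38% survival (21% lost) | 44% | 55% |
| 6.7-month median (27% lost) | 39% | 52% |

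**Exactly one of six unassessed.** P(X ≥ 3) with X ~ Bin(5, p): 50% instead of 66% at a true 50%, and 21% instead of 32% at 33%. At 78% survival, the chance that at least one of six dies by 3 months is 1 − (1 − 0.0602)^6 = 31%.

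**Effect of an evaluable denominator.** If no DLT is seen before loss, six evaluable patients restore the no-loss column. If every early DLT is recorded and kept while event-free losses are dropped, the rate among evaluable patients is p / [p + (1 − p)(1 − d)]. At a true 50% this is 0.5 / (0.5 + 0.5 × 0.940) = 52%, P(stop) 68%, at 78% survival. At 38% survival it is 0.5 / (0.5 + 0.5 × 0.785) = 56%, P(stop) 76%. These are the most that this bias can add in each scenario.

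**Replacements.** At 78% survival, 6/(1 − d) = 6.4 patients are enrolled on average to reach six evaluable. The chance that no more than one replacement is needed is P(Bin(7, 0.0602) ≤ 1) = 94%.

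**The case against.** The strongest reply is that few patients would be lost unassessed and that much early toxicity would be recorded anyway. Much of this stands.

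- CNS toxicity is largely managed on study. In 7.0.2, discontinuation for grade 2–3 necrosis, seizure or cognitive events comes only if "Toxicity does not resolve within 12 weeks of last dose" or, for some of these events, if steroids cannot be reduced.
- On early discontinuation, "all applicable activities scheduled for the final trial visit should be performed at the time of discontinuation" (13.1.1.13).
- SAE reporting runs for 90 days after treatment stops (13.2.3.1). Even a patient who stops after cycle 1 is covered to about 3 months, unless new therapy shortens the window, consent is withdrawn or contact is lost.
- Exit for progression before the 3-month reading is limited: 6.5 places the first progression scan at week 12 and allows treatment until confirmation, and 11.1.11 continues pembrolizumab after new CNS lesions.
- A death from CNS toxicity would plausibly count as a DLT, being grade 5 in the Section 8.0 table.

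This makes the gap smaller but does not close it. Adverse-event reporting records events; it does not say how the gate scores a patient with no 3-month assessment. Death from other causes, withdrawal, loss to follow-up and early new therapy remain. The pembrolizumab-alone study cited in 4.4.1 had 4 of 18 patients (22%) not evaluable. That is only indicative, since the reasons given were hemorrhage and extracerebral progression in a study without SRS.

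A reader might also infer that the plan scores lost patients as DLT-free. It does not say so; that is the effect of the fixed denominator. For late necrosis, 14.3.4 already handles death and censoring, and late toxicity cannot stop an arm. What remains there is only that 14.3.1 adds a crude rate out of 12 and neither estimate is named as governing.

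**Conclusion.** The point holds as an omission that biases the primary safety reading in one direction, and it should be fixed. Confidence is high on the omission and lower on its size, because the plan states no loss rate.

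At the plan's expected survival and its own DLT rates, the chance of stopping an arm drops by 2 to 4 percentage points; at a true rate of 50% it drops by about 6. These figures rest on constant hazard, loss independent of toxicity and no DLT seen before loss. Constant hazard may overstate early deaths in asymptomatic patients with ECOG 0–1, whereas withdrawal would add losses.

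A reader might infer that the gate largely fails, with P(stop) at a true 50% falling to 44% or 39%. The documents do not support that as the expected case. Those figures come from survival without the combination, and they shrink to 55% and 52% if half of the lost DLT patients are seen first. Nor is 38% survival an upper bound: the 6.7-month median gives more loss. Both are scenarios.

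**What to change.** 1. In 2.3 and 14.1.1, read the gate on six DLT-evaluable patients: those with a DLT recorded by 3 months, or assessed at 3 months. Replace non-evaluable patients and keep the protocol's threshold of 3. Say whether replacements use that arm's expansion slots within the total of 30. State how death before 3 months, and severe CNS symptoms still present at last contact, are counted, consistently with 3.1.3.
2. In 14.3.1, report the acute rate and Clopper-Pearson interval over evaluable patients. Beside it, show the all-enrolled rate and a worst case that counts unassessed patients as DLTs.
3. For necrosis at 6 and 12 months, name the 14.3.4 cumulative incidence as the governing estimate over the crude rate out of 12.

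The cost is mainly wording and some delay. A gate may wait for a replacement and that patient's 3 months: at 78% survival there is a 31% chance that any is needed and a 94% chance that no more than one is. Replacements are treated before the gate is read. Keeping early DLTs while dropping event-free losses can push the rate slightly up, which is why the all-enrolled rate belongs beside it.
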